5.7. Safety Analyses

The safety and tolerability of treatment will be assessed by the followings:

- Adverse events
- Suicide-related thoughts and behaviors
- Vital signs and weight
- Laboratory measurements
- ECGs
- Assessment of Driving Incidents

For vital signs, weights, and labs, the baseline value is defined as the last non-missing value before or at Visit 2.

The post-baseline value is defined as the last measurement on EoS/Visit 3. Note that this study does not have any unscheduled visit and associated measurement. Therefore, there is only one post-baseline values. However, if there are multiple post-baseline values, then the last measurement on EoS/Visit 3 will be used for continuous analysis and all values after dosing will be considered as post-baseline values for categorical analysis.

5.7.1. *Adverse Events*

AEs will be coded by the latest Medical Dictionary for Regulatory Activities (MedDRA) version at the timing of the final DBL.

AEs are collected from Visit 1 to Visit 3.

An AE with the time of onset on or within 48 hours after a dose of study drug, or an event that worsens in intensity within 48 hours of a dose of study drug will be considered a treatment-emergent adverse event (TEAE).

Post-dose AEs are defined as the same as the TEAE except without the restriction of the 48 hours cutoff.

For each TEAE, the reported severity of the event (mild, moderate, or severe) will be determined by physicians. The Medical Dictionary for Regulatory Activities (MedDRA) Lowest Level Term (LLT) will be used in the treatment-emergent computation. For each patient and TEAE, the maximum severity for the MedDRA level being displayed (preferred term, High Level Term,

or system organ class [SOC]) is the maximum postbaseline severity observed from all associated LLTs mapping to that MedDRA level.

Serious Adverse Events (SAE) are defined in PROTOCOL Section 9.2.1.

Treatment Emergent SAE (TESAE) is an SAE which occurs within 48 hours after a dose of study drug.

Following summary will be created:

- Overview of AEs (including death, SAE, TESAE, Discontinuations from Study due to an Adverse Event, AE, post-dose AE, TEAE, TEAE related to study treatment)
- TEAEs
 - By PT by decreasing frequency
 - By PT by decreasing frequency with an incidence in any lasmiditan group $\geq 1.5\%$ (common TEAE) and PT including “Vertigo”.
 - By SOC/PT (sorted alphabetically by system organ class (SOC), then by frequency in preferred term (PT))
 - By maximum severity/PT
- Post-dose AEs
 - By PT by decreasing frequency
 - By SOC/PT (sorted alphabetically by system organ class (SOC), then by frequency in preferred term (PT))
- TEAEs by PT considered to be related to investigational product by investigator
- TESAEs by PT
- TESAEs by PT considered to be related to investigational product by investigator
- SAEs by PT

Listing of AE (with TEAE flag) will be created for all randomized population

List of SAE will be created.

Note: If multiple severities are reported for a given AE and subject, then the most severe intensity will be counted. The same rule is applied for TEAEs.

Note: Patients were told not to report symptoms that usually occurred during migraine attacks (e.g. nausea).

Note: For events that are gender-specific, the denominator and computation of the percentage will include only patients from the specific gender.

5.7.2. *Columbia-Suicide Severity Rating Scale (C-SSRS)*

The C-SSRS will be used to assess suicidal ideation, suicidal behavior, and self-injurious behavior without suicidal intent. At Visit 1, the screening version will be used to assess suicidal ideation and behavior during the lifetime and in the past one month. At the following visits (Visit 2, EOS/Visit 3), the Since Last Visit version will be used to assess suicidal ideation and behavior since the last visit.

The following outcomes are C-SSRS categories and have binary responses (yes/no).

Category 1 – Wish to be Dead

Category 2 – Non-specific Active Suicidal Thoughts

Category 3 – Active Suicidal Ideation with Any Methods (Not Plan) without Intent to Act

Category 4 – Active Suicidal Ideation with Some Intent to Act, without Specific Plan

Category 5 – Active Suicidal Ideation with Specific Plan and Intent

Category 6 – Preparatory Acts or Behavior

Category 7 – Aborted Attempt

Category 8 – Interrupted Attempt

Category 9 – Actual Attempt (non-fatal)

Category 10 – Completed Suicide

Self-injurious behavior without suicidal intent is also a C-SSRS outcome (although not suicide-related) and has a binary response (yes/no).

Composite endpoints based on the above categories are defined below.

- Suicidal ideation: A “yes” answer at any time during treatment to any one of the five suicidal ideation questions (Categories 1-5) on the C-SSRS.
- Suicidal behavior: A “yes” answer at any time during treatment to any one of the five suicidal behavior questions (Categories 6-10) on the C-SSRS.
- Suicidal ideation or behavior: A “yes” answer at any time during treatment to any one of the ten suicidal ideation and behavior questions (Categories 1-10) on the C-SSRS.

Summary of 10 categories and “Self-injurious behavior without suicidal intent” will be created for baseline (Visit 1 and Visit 2 separately) for safety population and for all randomized population.

Summary of 10 categories and “Self-injurious behavior without suicidal intent”, and 3 composite endpoints will be summarized will be created for post baseline for safety population and for all randomized population.

Listings will present all C-SSRS data for subjects with at least one positive response to any C-SSRS question at any time during the study for all randomized population

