9.2.1. Serious Adverse Events

An SAE is any AE from this study that results in one of the following outcomes:

- Death.
- Initial or prolonged inpatient hospitalization.
- A life-threatening experience (that is, immediate risk of dying).
- Persistent or significant disability/incapacity.
- Congenital anomaly/birth defect.

- Important medical events that may not be immediately life-threatening or result in death or hospitalization but may jeopardize the patient or may require intervention to prevent one of the other outcomes listed in the definition above. Examples of such medical events include allergic bronchospasm requiring intensive treatment in an emergency room or at home, blood dyscrasias or convulsions that do not result in inpatient hospitalization, or the development of drug dependency or drug abuse.

All AEs occurring after signing the ICF are recorded in the eCRF and assessed for serious criteria. The SAE reporting to the sponsor begins after the patient has signed the ICF and has received investigational product. However, if an SAE occurs after signing the ICF, but prior to receiving investigational product, the SAE should be reported to the sponsor as per SAE reporting requirements and timelines (see Section 9.2) if it is considered reasonably possibly related to study procedure.

Study site personnel must alert Lilly or its designee of any SAE within 24 hours of investigator awareness of the event via a sponsor-approved method. Once the SAE eCRF form is initiated, an email is automatically triggered to the sponsor's global patient safety department.

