5.7.6. Assessment of Driving Incidents

Assessment of accidents/violations will be listed by patient (all randomized population). Summary table will be created (baseline and postbaseline)

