- Ischaemic heart disease (includes sub-SMQs; SMQ 20000043)
- Pulmonary hypertension (SMQ 20000130)
- Torsade de pointes/QT prolongation (SMQ 20000001)

The list of events and individual patient data were then medically reviewed to determine if the terms identified represented likely CV AE. For example, if an AE term “edema” was identified using the “Cardiac failure” SMQ broad list in a patient who experienced this AE after taking the study drug, and at the same time also reported dyspnea, had a medical history of hypertension, was taking concomitant ace-inhibitor + hydrochlorothiazide, or recently started a separate diuretic, then based on this information the AE of “edema” would represent a likely CV AE.

The listing of all potential CV AEs with reason(s) for whether or not the events were considered likely CV is provided for all randomized population. Events that are “treatment emergent” are flagged.

Following summary will be created:

- Summary and Analysis of Potential CVAE within SMQ
- Summary and Analysis of Likely CVAE within SMQ, PT
- Summary and Analysis of Likely CVTEAE within SMQ, PT
- Summary and Analysis of Potential CVAE by CVRFs by SMQ
- Summary and Analysis of Likely CVAE by CVRFs by PT
- Summary and Analysis of Likely CVTEAE by CVRFs by PT

- Patient Listing for Likely CV AEs in Patients with Categorical Changes of Interest in Vital Signs (Pulse, SBP, DBP)
- Summary and Analysis of Likely Cardiovascular Adverse Events in Patients with Categorical Changes of Interest in Blood Pressures and Pulse.

Note: In this analysis, patients with a categorical change of interest in BP or pulse (defined in [Table LAIH. 5.4](#)) are used as the denominator whereas the numerator represents the number of patients reporting a likely CV AE. The summary is based on

- SMQ
- Patients with at least one Narrow scope PT in the SMQ
- Patients with at least one Narrow or Broad scope PT in the SMQ

Concomitant Cardiovascular Medications

Cardiovascular medications were identified using the World Health Organization's ATC/Defined Daily Dose codes from a listing of all concomitant medications. These were summarized based on ATC2 codes within the "Cardiac System," as well as medications within the ATC2 code of "Antithrombotic agents" in the categories as described in [Table LAIH. 5.5](#).

Table LAIH. 5.5 Identified Cardiovascular Medications Anatomical Therapeutic Chemical (ATC)/Defined Daily Dose

C01, Cardiac Therapy	C07, Beta-Blocking Agents

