5.7.7.2. Hepatic Safety

The percentages of patients with potentially drug-related hepatic disorders were summarized by treatment using the MedDRA PTs contained in any of the following SMQs, separately for AEs and TEAEs. Cases were then subsequently medically reviewed:

- Broad and narrow terms in the Liver-related investigations, signs, and symptoms (SMQ 20000008)
- Broad and narrow terms in the Cholestasis and jaundice of hepatic origin (SMQ 20000009)
- Broad and narrow terms in the Hepatitis, noninfectious (SMQ 20000010)

- Broad and narrow terms in the Hepatic failure, fibrosis, and cirrhosis and other liver damage (SMQ 20000013)
- Narrow terms in the Liver-related coagulation and bleeding disturbances (SMQ 20000015)

Hepatic events (AEs which can be beyond 48 hours) in the above SMQs will be summarized for safety population.

Treatment-emergent hepatic events in the above SMQs will be summarized for safety population.

Hepatic events (AEs which can be beyond 48 hours) listing with TEAE flag will be created for safety population.

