5.7.7.3. Injuries and Accidents Secondary to Neurologic Adverse Events

In order to accurately capture reported injuries and accidents, all AEs in the Injury, Poisoning, and Procedural Complications SOC were reviewed. These AEs were not limited to a treatment-emergent time period (that is, 48 hours postdose). Each AE of injury, poisoning, and procedural complication was medically reviewed in order to determine if a neurologic TEAE (from the Nervous system disorders SOC) either preceded or occurred concurrently with the AE.

Following TFL will be created.

- Listing of Neurologic TEAE (already medical reviewed),
where “Neurologic TEAE timing <= injury timing”
- Listing of Neurologic TEAE (NOT medical reviewed),
where “Neurologic TEAE timing <= injury timing”
- Summary of “Neurologic TEAEs” and “AEs SOC=Injury, Poisoning, and Procedural Complications”
- Summary of all PTs related to the Injury, Poisoning, and Procedural Complications SOC

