5.7.7.4. Suicidal Ideation and Behavior and Nonsuicidal Self-Injurious Behavior

A summary table of PTs within the Suicide/Self Injury SMQ (20000037) is provided for safety population. All AEs are presented (after Visit 1 through Visit 3.)

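### Several special-topic AE summaries (suicide/self-injury, cardiovascular, hepatic, injury) have no post-dose lower bound, so events before the single dose can enter every arm's column, placebo included

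*SAP*

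**What the plan says.** SAP 5.7.1 works with three AE windows. The widest is "AEs are collected from Visit 1 to Visit 3". The narrowest is the treatment-emergent AE (TEAE), with onset or worsening within 48 hours of the dose. Between them, "Post-dose AEs are defined as the same as the TEAE except without the restriction of the 48 hours cutoff". The intermediate set is used only in the overview and in the general tables by preferred term (PT) and by system organ class (SOC) and PT.

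Protocol 9.2.1 confirms that pre-dose events are in the database: "All AEs occurring after signing the ICF are recorded in the eCRF and assessed for serious criteria".

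The special-topic sections then specify:

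- Suicide/self-injury SMQ (SAP 5.7.7.4): "All AEs are presented (after Visit 1 through Visit 3".
- Cardiovascular (5.7.7.1): "Summary and Analysis of Likely CVAE within SMQ, PT", together with potential-CVAE summaries and versions by risk factor. Only the likely-CV summaries have treatment-emergent counterparts.
- Hepatic (5.7.7.2): "Hepatic events (AEs which can be beyond 48 hours) in the above SMQs will be summarized for safety population". A treatment-emergent summary is also planned.
- Injury (5.7.7.3): "Summary of all PTs related to the Injury, Poisoning, and Procedural Complications SOC", with injury AEs not confined to the 48-hour period.
- Driving (5.7.6): "Summary table will be created (baseline and postbaseline".

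Under SAP 5.3 and 5.4, safety tables show placebo, each lasmiditan dose and all lasmiditan combined. Patients in the safety population are grouped by the drug they used.

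**The concern.** Each patient takes one dose, so an event that started and ended before it cannot have been caused by it. A table by treatment that includes screening and waiting-period events mixes background with the period of interest. The topics affected are those singled out for closer safety review, where counts are likely to be small.

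The hepatic wording suggests that the aim was to look past 48 hours after the dose. The rule as written also opens the window backwards to Visit 1. At stake is whether a reader of the cardiovascular or hepatic tables can see what happened between 48 hours after the dose and Visit 3.

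**Working it through.** The documents give no figure to reproduce here. The check has three parts: which tables have a lower bound, how long the windows are, and what the mixing does to a comparison.

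**1. Lower bound and companion tables**

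| Summary | Lower bound stated? | Treatment-emergent companion? |
|---|---|---|
| Suicide/self-injury SMQ | No; Visit 1 to Visit 3 is explicit | None |
| Potential CVAE (by SMQ; by risk factor) | No | None |
| Likely CVAE | No | Yes, to 48 h |
| Hepatic AEs | No | Yes, to 48 h |
| Injury-SOC PTs | No | Listings require a neurologic TEAE at or before the injury; the general post-dose SOC/PT table covers the same SOC |

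For the cardiovascular and hepatic SMQ groupings, subtracting the TEAE table from the AE table leaves pre-dose events and events after 48 hours together. The general post-dose tables do not apply the SMQ groupings. The listings in 5.7.1, 5.7.7.1 and 5.7.7.2 specify only a treatment-emergent flag, which does not separate the two either. This matters most for hepatic events: the SAP revision history says that Visit 3 laboratory tests generally fall more than 48 hours after dosing.

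**2. Window lengths for dosed patients** (Protocol 5.1)

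- Visit 1 to Visit 2: 7 to 30 days. Visit 2 to dose: 0 to 56 days. Pre-dose total: 7 + 0 = 7 to 30 + 56 = 86 days.
- Dose to Visit 3: 3 to 28 days.

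At a constant background rate, the pre-dose share is pre / (pre + post):

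- Minimum: 7 / (7 + 28) = 20%.
- 28 days before, 14 after: 28 / 42 = 67%.
- 42 days before, 14 after: 42 / 56 = 75%.
- Maximum: 86 / (86 + 3) = 97%.

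The two middle cases are assumptions. The documents do not give actual waiting times.

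**3. Effect on a comparison** (illustrative risks, not from the documents)

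Let p be the post-dose risk and b a pre-dose risk equal in all arms. The all-AE risk is 1 − (1 − b)(1 − p). Take p = 0.5% on placebo and 2.0% on active.

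| b | Placebo | Active | Risk ratio | Risk difference (points) |
|---|---|---|---|---|
| 0 | 0.50% | 2.00% | 4.00 | 1.50 |
| 0.5% | 1.00% | 2.49% | 2.50 | 1.49 |
| 1% | 1.50% | 2.98% | 1.99 | 1.49 |
| 2% | 2.49% | 3.96% | 1.59 | 1.47 |

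Rates rise in both arms, the ratio moves toward 1 and the difference barely changes. With the planned treated arms of 190, 81, 190 and 163, a single stray event is 1/81 = 1.2% of the 50 mg arm but 1/190 = 0.5% of placebo. Chance can therefore disturb an apparent dose pattern.

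**The case against.** The strongest reply is that much of this is already covered. TEAE and post-dose AE tables are planned by PT and by SOC/PT. Likely-CV and hepatic events have treatment-emergent summaries. Injury AEs are medically reviewed against a preceding or concurrent neurologic TEAE. Likely CV events are selected on individual patient data, and the worked example in 5.7.7.1 concerns an event after study drug. Safety is descriptive, with no tests. In the hypersensitivity section (5.7.7.5), AEs are tabulated as beyond 48 hours, so the authors may have meant the same for hepatic events. Some early events would also keep a patient from being dosed. For example, exclusion criterion 17 covers specified suicidal ideation or behaviour in the month before Visit 1 or 2.

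Most of this stands and limits the point. The injury gap is confined to the SOC summaries, and post-dose injury PTs can be read from the general table. For all topics except suicide/self-injury, the fault is a missing lower bound and not an explicit inclusion. Medical review may remove some pre-dose cardiovascular cases, but no timing rule is written. None of it supplies a cardiovascular or hepatic SMQ table for post-dose events after 48 hours, or a dose-anchored version of the suicide/self-injury and potential-CVAE tables.

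Three stronger readings are tempting and not supported:

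- *Pre-dose events are counted against lasmiditan.* The placebo column takes them in too, and the arms are randomised and blinded. The expected effect is dilution.
- *The SAEs-by-PT table is a mistake.* SAP 5.11 counts an event as serious whether or not it is treatment-emergent, and treatment-emergent SAE tables sit beside it. An all-SAE table is a normal reporting choice.
- *The driving summary has the same fault.* Read by visit, post-baseline would start at Visit 2, up to 8 weeks before the dose. But 5.7.6 does not define the term, and the documents do not show that incident dates are collected.

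**Conclusion.** The point holds in limited form. As written, the suicide/self-injury table explicitly, and the potential and likely CV, hepatic and Injury-SOC summaries through the absence of a lower bound, can include events before the dose in every arm. Under a constant background rate, between 20% and 97% of background events in these tables would precede the dose. That range rests on window lengths alone, and events that stop a patient from being dosed would lower it. The result is inflated absolute rates, ratios diluted toward 1 and noise in rare events. A reader might infer a bias against lasmiditan; the documents give no basis for that. The main practical loss is that post-dose cardiovascular and hepatic SMQ events after 48 hours cannot be read from any planned table. Severity is minor to moderate.

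**What to change.** - In SAP 5.7.7.1 to 5.7.7.4, base the by-treatment AE summaries on the post-dose AE set already defined in 5.7.1, and keep the TEAE versions. That definition retains pre-existing events that worsen after the dose.
- Show pre-dose events in a separate row, or in the listings with a pre-dose/post-dose flag beside the TEAE flag.
- Keep the SAEs-by-PT table as an all-SAE table and add a post-dose SAE count.
- In 5.7.6, define post-baseline. Only if incident dates are available, report incidents after Visit 2 separately before and after the dose.

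The cost is SAP wording, one extra filter and a few extra rows. No data are lost. The driving split is a separate task, because those data come from a questionnaire and not from AE records.

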Lasmiditan is generally well tolerated. In the Phase 3 studies, a TEAE was defined as an event that first occurred or worsened in severity after baseline and within 48 hours of a first or second dose (if applicable) of study drug. The most common TEAEs reported in Study LAHJ/301 and Study LAHK/302 for the 100 mg and 200 mg treatment groups were: dizziness (15.4% to 17.2%); paresthesia (5.8% to 7.2%); somnolence (5.1% to 6.0%); fatigue (4.1% to 4.0%) and nausea (3.2% to 3.9%). The majority of the TEAEs were mild or moderate in severity and self-limiting with a short duration.

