5.4. Justification for Dose

Three doses (lasmiditan 50 mg, 100 mg, and 200 mg) used in the Study 302/LAHK (study for bridging reference), have been selected in this Study LAIH in Japanese patients with migraine. Two single-attack Phase 3 studies (Study 301/LAHJ and Study 302/LAHK) of lasmiditan have been completed, and these studies show dose-dependent efficacy of lasmiditan versus placebo to increase freedom from headache pain with lasmiditan. All doses (50 mg, 100 mg, and 200 mg) showed statistically significant superiority versus placebo on pain freedom, MBS freedom, and pain relief. In general, the efficacy of lasmiditan was dose dependent, with lasmiditan 50 mg showing the least efficacy and lasmiditan 200 mg showing the most efficacy. Safety analysis showed TEAEs were increased with lasmiditan compared to placebo, with the most common AEs being dizziness, paresthesia, somnolence, fatigue, and nausea. In general, these TEAEs were observed to increase in a dose-dependent manner (i.e., they were lowest with lasmiditan 50 mg and highest with lasmiditan 200 mg). These TEAEs were usually mild to moderate in severity with a median duration of 1 to 5 hours.

6. Study Population

Prospective approval of protocol deviations to recruitment and enrollment criteria, also known as protocol waivers or exemptions, are not permitted.

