9.1.2. Secondary Efficacy Assessments

Patient Diary

Other efficacy data will also be collected in the eDiary.

At the time points, 0 (pre dose), 0.5, 1, 1.5, 2, 3, 4, 24, and 48 hours, patients will assess the presence or absence (yes or no) of accompanying symptoms: photophobia, phonophobia, nausea, and vomiting. At time 0 (pre dose) patients will select from the accompanying symptoms present (from nausea, phonophobia, or photophobia only) the one that is the most bothersome to them.

Patients will also be asked to record the time of meaningful relief and the time at which they become headache pain free. At 2 and 24 hours after the study drug, patients will be asked to record their Patient Global Impression of Change (PGI-C) using a 7-point scale (very much better, much better, a little better, no change, a little worse, much worse, and very much worse). The eDiary assessments are listed in Appendix 5.

Patients will record details of AEs, concomitant medication use, and any other relevant information in the patient's paper diary and these will be reviewed at the next visit.

Recording Use of Rescue/Recurrence Medication: Refer to Section 7.2.1.1 for details.

Migraine Quality of Life Questionnaire (MQoLQ): The 24-hour Migraine Quality of Life Questionnaire (24-hr MQoLQ) has been specifically developed to measure the Health-Related Quality of Life of patients with migraine within a 24-hour period after having taken migraine medication. The 24-hour MQoLQ is a 15-item, self-administered questionnaire. The items cover 5 domains (work functioning, social functioning, energy and vitality, feelings and concerns, and migraine symptoms) (Hartmaier et al. 1995; Santanello et al. 1995, 1997). Each domain consists of 3 questions answered on a 7-point scale where 1 indicates maximum impairment and 7 indicating no impairment. A domain score is calculated by summing the responses to the 3 questions and the domain score ranges from 3 to 21. The questionnaire will be administered 24 hours after the study drug.

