9.2. Adverse Events

Investigators are responsible for monitoring the safety of patients who have entered this study and for alerting Lilly or its designee to any event that seems unusual, even if this event may be considered an unanticipated benefit to the patient.

The investigator is responsible for the appropriate medical care of patients during the study.

Investigators must document their review of each laboratory safety report.

The investigator remains responsible for following, through an appropriate health care option, AEs that are serious or otherwise medically important, considered related to the investigational product or the study, or that caused the patient to discontinue the investigational product before

completing the study. The patient should be followed until the event resolves, stabilizes with appropriate diagnostic evaluation, or is reasonably explained. The frequency of follow-up evaluations of the AE is left to the discretion of the investigator.

Lack of drug effect is not an AE in clinical studies, because the purpose of the clinical study is to establish treatment effect.

After the ICF is signed, study site personnel will record via electronic case report form (eCRF) the occurrence and nature of each patient's preexisting conditions, including clinically significant signs and symptoms of the disease under treatment in the study. In addition, site personnel will record any change in the condition(s) and any new conditions as AEs. Investigators should record the following via eCRF for each AE: time of onset, time of termination, severity, and their assessment of the potential relatedness of each AE to protocol procedure and investigational product.

The investigator will interpret and document whether or not an AE has a reasonable possibility of being related to study treatment or a study procedure, taking into account the disease, concomitant treatment or pathologies.

A "reasonable possibility" means that there is a cause and effect relationship between the investigational product, study device and/or study procedure and the AE.

The investigator answers yes/no when making this assessment.

Planned surgeries and nonsurgical interventions should not be reported as AEs unless the underlying medical condition has worsened during the course of the study.

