5.6.3. Details of Efficacy Analyses

Table LAIH. 5.3 is the list of primary/ key secondary/ other secondary/ exploratory analysis with each analysis population, timeframe and analysis method.

Table LAIH. 5.3 Primary, Key Secondary, Other Secondary and Exploratory Efficacy Variables and Analysis Methods

ID	Type	efficacy variables	POP	Timeframe	Analysis
1	PRIM /2 ND	Headache Pain Free	mITT/ ITT/ PPS	up to 48h	LOGISTIC
2	2KEY	Pain Free Trend Test	mITT/ ITT/ PPS	2h	CA
3	2KEY /2ND	Headache Pain Relief	mITT/ ITT/ PPS	up to 48h	LOGISTIC
4	2 ND	MBS-Free	mITT/ ITT/ PPS	up to 48h	LOGISTIC
5	2 ND	Migraine Symptoms Present at Assessment Times (Nausea, Phonophobia, Photophobia, Vomiting)	ITT	up to 48h	LOGISTIC
6	OTH	MBS-Free by Chosen Symptom: (Nausea, Phonophobia, Photophobia)	ITT	up to 48h	LOGISTIC
7	2 ND	Time to Headache Pain Free Through 48 Hours Post-Dose	ITT	up to 48h	KM
8	2 ND	Time to Headache Pain Relief Through 48 Hours Post-Dose	ITT	up to 48h	KM
9	2 ND	Time to MBS-Free Through 48 Hours Post-Dose	ITT	up to 48h	KM
10	OTH	Time to MBS-Free by Chosen Symptom Through 48 Hours Post-Dose: (Nausea, Phonophobia, Photophobia)	ITT	up to 48h	KM
11	2 ND	Disability	ITT	0.5h/1h/2h/24h	LOGISTIC

12	OTH	Incidence of Rescue or Recurrence Medication Use	ITT	[0h-2h]/ [2h-24h]/ [24h-48h]	LOGISTIC
13	OTH	Incidence of Headache Recurrence Through 24/48 Hours Post-Dose	ITT	2h< recurrence <=24h 2h< recurrence <=48h	LOGISTIC
14	2 ND	PGI-C	ITT	2h/24h	LOGISTIC
15	2 ND	Sustained Pain Free at 24 Hours and 48 Hours	ITT	24h/48h	LOGISTIC
16	2 ND	Time to No Disability Through 24 Hours	ITT	up to 24h	KM
17	OTH	Summary of Symptom-Free at Assessment Times (Nausea, Phonophobia, Photophobia, Vomiting)	ITT	up to 48h	LOGISTIC
18	OTH	Total Migraine Freedom	ITT	up to 48h	LOGISTIC
19	OTH	Modified Sustained Pain Free at 24 Hours and 48 Hours	ITT	24h/48h	LOGISTIC
20	OTH	Time to Meaningful Pain Relief Through 48 Hours	ITT	up to 48h (including 6h/8h)	KM
21	OTH	Time to Pain Free Through 48 Hours	ITT	up to 48h (including 6h/8h)	KM
22	2 ND	Change from Baseline of EQ-5D-5L in Index Score	ITT	24h	ANOVA
23	2 ND	Change From Baseline of EQ-5D-5L in Visual Analog Scale	ITT	24h	ANOVA
24	2 ND	HRQoL Measured by MQoLQ in 5 Domains	ITT	24h	ANOVA
25	2 ND	Treatment Satisfaction	ITT	48h	CMH

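### TEAE tables can only under-count nausea, because patients were told not to report their usual attack symptoms, and no planned eDiary output shows nausea that is new after dosing

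*SAP*

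**What the plan says.** The note in SAP 5.7.1 reads: "Patients were told not to report symptoms that usually occurred during migraine attacks (e.g. nausea", with nausea as its example. It stands under the list of AE summaries and has no stated link to other outputs.

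Protocol 5.4 describes the earlier studies "with the most common AEs being dizziness, paresthesia, somnolence, fatigue, and nausea" and says these events generally rose with dose. Protocol 3.2 gives nausea rates of 3.2% to 3.9% for the 100 mg and 200 mg groups.

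Protocol 9.2 first has sites record preexisting conditions, which include clinically significant signs and symptoms of the disease under study. It then says "site personnel will record any change in the condition(s) and any new conditions as AEs".

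SAP 5.7.1 plans a TEAE table of all preferred terms and a shorter common-TEAE table, described as "By PT by decreasing frequency with an incidence in any lasmiditan group" of at least 1.5%, with vertigo terms kept in whatever their rate. The same cut-off selects terms for the severity, onset and duration summaries (SAP 5.7.7.7) and the intrinsic-factor tables (SAP 5.7.7.8).

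On the diary side, Protocol 9.1.2 says that before dosing and at eight later times up to 48 h "patients will assess the presence or absence (yes or no) of accompanying symptoms: photophobia, phonophobia, nausea, and vomiting". SAP Table LAIH. 5.3 analyses these data in the ITT population. ID 5 covers each symptom present at each time, whatever its baseline value. ID 17 covers each symptom absent at each time, with no baseline condition stated.

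**The concern.** A patient whose attacks usually bring nausea has no ready way to tell nausea caused by the drug from nausea caused by the attack. Someone following the instruction may leave both out. Reported nausea can therefore fall short of actual nausea but cannot exceed it because of the instruction. If the same share goes unreported in every arm, the active-minus-placebo difference shrinks by that share.

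Two things are at stake. The TEAE rate for a named reaction would be too low by an unknown amount. Nausea could also fall below the 1.5% cut-off and so lose its place in the severity, onset, duration and intrinsic-factor summaries, although it would still appear in the full table by preferred term. No efficacy conclusion is affected.

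The diary is the natural independent source, because every patient is asked about nausea directly. The planned diary analyses were built to show relief, not onset.

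**Working it through.** The plan states no figure on this point, so there is none to reproduce. The check has two parts.

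**1. The 1.5% cut-off**

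Inputs: planned treated patients of 81, 190 and 163 in the 50, 100 and 200 mg arms (SAP 5.2, where these are the mITT numbers; the safety population may be somewhat larger), and nausea at p = 3.2% to 3.9% (Protocol 3.2). The unreported share u is an assumption.

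- Patients needed to reach 1.5%: 0.015 × 190 = 2.85, so 3; 0.015 × 163 = 2.4, so 3; 0.015 × 81 = 1.2, so 2.
- Expected nausea TEAEs with full reporting: 190 × 0.032 = 6.1 to 190 × 0.039 = 7.4 at 100 mg; 163 × 0.032 = 5.2 to 163 × 0.039 = 6.4 at 200 mg.
- Chance that an arm reaches the cut-off: P(X ≥ 3) with X ~ Binomial(n, p(1 − u)).
- A term enters the table if any lasmiditan arm qualifies, so it drops out only if all arms miss. The last column multiplies the two chances of missing. For u = 50% and p = 3.2% this is (1 − 0.588) × (1 − 0.485) = 0.21.

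| u (assumed) | 100 mg reaches 1.5% | 200 mg reaches 1.5% | Both miss |
|---|---|---|---|
| 0% | 94%–98% | 90%–96% | 0.1%–0.6% |
| 25% | 84%–92% | 75%–86% | 1%–4% |
| 50% | 59%–72% | 48%–62% | 11%–21% |
| 75% | 20%–28% | 14%–21% | 56%–69% |

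The last column is an upper bound on dropping out, because the 50 mg arm could still qualify. The documents give no nausea rate for 50 mg.

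**2. Why IDs 5 and 17 do not show new nausea**

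Let s be the share without nausea at hour 0, e the chance that such a patient has nausea at a later time, and k the chance that a patient with nausea at hour 0 still has it then. ID 5 estimates

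P(nausea) = s·e + (1 − s)·k,

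and ID 17 is its complement. The active-minus-placebo difference is

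s·Δe + (1 − s)·Δk.

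A drug that causes nausea makes Δe positive. A drug that relieves migraine nausea makes Δk negative. The two cancel when Δe = ((1 − s)/s) × |Δk|. With s assumed at 30%, 50% and 70%, the multiplier (1 − s)/s is 0.7/0.3 = 2.3, 0.5/0.5 = 1 and 0.3/0.7 = 0.43. An excess of new nausea from 0.43 to 2.3 times the relief effect would therefore show as no difference.

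The other diary outputs do not help. The most-bothersome-symptom analyses for nausea (IDs 6 and 10) start from patients who already had nausea. Total migraine freedom (ID 18) combines pain and all symptoms.

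A table restricted to patients nausea-free at hour 0 estimates e directly. At s = 30% to 70% (assumed) its denominators would be 57 to 133 on placebo, 24 to 57 at 50 mg, 57 to 133 at 100 mg and 49 to 114 at 200 mg.

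**The case against.** The strongest reply is that the note is narrow, openly stated and compatible with the protocol. Protocol 9.2 treats symptoms of the disease as preexisting, so unchanged nausea that is usual for a patient is not an AE under that section either. Nausea that is new or worse for that patient is not excluded by the note's wording, and sites collect AEs themselves. This largely stands. A reader might infer a flat contradiction with Protocol 9.2, but the tension is partial. It lies in whether patients could tell usual nausea from changed nausea.

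Second, diary nausea and vomiting are already reported by arm. This also stands: the data are not unused, and ID 5 is not the only analysis of them. What is missing is a split by hour-0 status.

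Third, the proposed table has its own masking. A drug that stops the attack may also prevent migraine nausea that would otherwise have begun, so fewer migraine cases can offset drug-caused ones. After 2 h, permitted antiemetics and analgesics blur the picture further, perhaps unequally by arm. This stands too. It limits what the table can show and is the reason to end the main display at 2 h.

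**Conclusion.** The point holds as a reporting gap with an inexpensive remedy. The direction of the error is certain: the instruction can lower the nausea TEAE count and cannot raise it. Its size cannot be determined from the documents. The cut-off chances rest on taking 3.2% to 3.9% as the true rates, on the planned arm sizes and on assumed unreported shares. They show that nausea could leave the common-TEAE outputs, not that it will.

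Three stronger readings are not supported:

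- A reader might infer that comparison with the earlier studies is biased. The documents do not say how those studies collected nausea. If they gave the same instruction, the comparison is like for like and 3.2% to 3.9% is itself too low.
- A reader might infer a specific number of missed cases per arm. No figure in the documents supports one.
- A reader might infer that drug-caused vomiting is under-counted too. Vomiting is a migraine symptom the instruction may cover, but Protocol 3.2, 3.3 and 5.4 do not list it among the common reactions.

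**What to change.** Add to SAP 5.7.1 one descriptive table by arm. Its population is safety-population patients with eDiary data who record no nausea at hour 0. Its outcome is nausea recorded at 0.5, 1, 1.5 or 2 h, as count and percentage, which precedes permitted rescue. Show 3 and 4 h separately, flagged for rescue or antiemetic use. Give the same display for vomiting as supportive.

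From the nausea row of the TEAE tables, cross-refer to this table and to IDs 5 and 17. Add a footnote stating the reporting instruction and where it was given to patients.

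There is precedent: SAP 5.7.7.7 already puts diary-based outcomes (2-hour interference with activity and PGI-C) into the dizziness and vertigo safety summaries.

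The cost is one table and a footnote, with no new data collection. The downsides should be printed with the table: the item is yes/no without severity or causality; the denominator is only patients nausea-free at hour 0; and prevention of migraine nausea can still mask drug-caused nausea. An excess over placebo is informative, but its absence is not reassurance. The table cannot undo what patients were told.
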